6 STUDY INTERVENTION(S) OR EXPERIMENTAL MANIPULATION(S)

6.1 STUDY INTERVENTION(S) OR EXPERIMENTAL MANIPULATION(S) ADMINISTRATION

6.1.1 STUDY INTERVENTION OR EXPERIMENTAL MANIPULATION DESCRIPTION

Person-family dyads assigned to both the intervention and control groups will receive usual care, comprising standard primary care at participating practices. Usual care involves following patients at variable intervals, with routine visits scheduled at 2 weeks-6 months, depending on the stability of health status. All patients may register for the patient portal, provide their primary care clinician / clinic with a completed advance directive to be uploaded in their electronic health record, or avail themselves of advance care planning with their primary care clinician or other clinic staff. However, these processes generally occur on an ad-hoc basis and do not involve a protocolized approach to engaging with family caregivers or advance care planning.

Person-family dyads assigned to the control group will receive a protocol of minimally enhanced usual care, encompassing an introductory letter (**F1B**), a print educational brochure (**F6**) and blank easy to complete advance directive (**F4, F5**). The educational materials include a 44-page brochure developed by the National Institute on Aging entitled “A Guide for Older People: Talking with your Doctor” (**F6**)⁶¹ and an easy-to-read advance directive (**F4, F5**). Control dyads will be told that they are participating in a study about communication in primary care. We chose an active control arm for several reasons: 1.) because providing an advance directive should be the standard of care even if it is often not ‘usual care’, 2.) to ensure that positive results can be attributed to the effectiveness of the intervention, and 3.) to mitigate perceptions among dyads randomized to the control group that they are not being offered anything beyond usual care.

Person-family dyads assigned to the intervention protocol will receive usual care in addition to SHARE, encompassing the following four components (see exhibit below).

1. An invitation from the primary care clinic introducing the intervention to prepare patients and families to engage in advance care planning discussions (**F1A, F7**),²⁴
2. Access to an ACP facilitator/ interventionist trained in the protocol and leading advance care planning for persons with cognitive impairment and their families,^{26,27}
3. Person-family agenda-setting to align perspectives about the role of family and stimulate discussion about health care issues and advance care planning (**F2**),²⁸ and
4. Education about communication and available resources, including a 44-page brochure developed by the National Institute on Aging entitled “A Guide for Older People: Talking with your Doctor” (**F6**),⁶¹ a blank advance directive (**F4, F5**, and information about and facilitated registration for the patient portal to enable and extend electronic interactions and information access to patients and family (**F3**).^{29,30}

SHARE Therapeutic Components, Content, Rationale, Evidence of Effectiveness

| Content | Rationale | Evidence of Effectiveness |
|---------|-----------|---------------------------|
|---------|-----------|---------------------------|

| | | |
|---|--|--|
| 1. Primary care initiated voluntary ACP | Most patients expect primary care practices to initiate ACP. ⁵³ Proactively introducing ACP normalizes these discussions. | Primary care initiatives to increase advance directive completion are effective and well-received. ^{24,62} |
| 2. ACP education and availability of non-clinician led ACP discussions | ACP education and resources increase patient & family awareness, knowledge and skill. ^{50,51} Respecting Choices is a structured educational program to train facilitators to facilitate ACP discussions. ^{25,63} | ACP is associated with delivery of goal concordant care, greater confidence among surrogate decision-makers ^{13,64-66} & reduced EOL costs. ^{25-27,63} |
| 3. Person-Family Agenda Setting | Individuals & families often have different concerns. Agenda-setting stimulates discussions about ACP & the role of family. | Agenda-setting helps clarify concerns, goals, and expectations, and increase engagement in care. ^{28,67,68} |
| 4. Education about communication resources, including access to Electronic Health Record Via Patient Portal | The patient portal facilitates timely and accurate information about patient health, diagnoses, test results, & prescribed treatments. Families are provided their own identity credentials to access information and communicate with clinicians. | The patient portal operates through mechanisms of convenience, continuity, activation, and understanding. ⁴³ Prior studies find clinical benefit of supporting family through technology. ^{69-73 30} |

ACP=advance care planning; EOL=end-of-life; PCP=primary care practice

6.1.2 ADMINISTRATION AND/OR DOSING

Staff at participating primary care clinics will be informed about the study objectives and how to respond to patient/family queries that may arise related to intervention processes such as how to facilitate registration to the patient portal for families, and where and how to upload a completed advance directive. Investigators will identify a liaison from each of the two partnering health systems to assist with the implementation of the intervention at participating clinics. Clinic staff at participating primary care clinics will be introduced to the study at monthly staff meetings.

Intervention and control dyads will be introduced to their respective protocol remotely (see section 5.5.2 for more information about telemedicine for remote processes) after randomization and completing the baseline enrollment survey. Study participants in both groups will be told they are participating in a study about communication in primary care and will be followed for up to 24 months. Research staff will provide person-family dyads in both groups with a letter from the primary care practice describing a new communication initiative.

Person-family dyads assigned to the **control** group will receive a protocol of minimally enhanced usual care, encompassing an introductory letter (**F1B**), print educational brochure (**F6**) and blank easy to complete advance directive (**F4, F5**).

Person-family dyads assigned to the intervention protocol will receive usual care in addition to SHARE. Research staff will provide patients with the contact information of the SHARE advance care planning facilitators (the interventionists) (**E9**), and will provide interventionists with the name, age, caregiving relationships, preferred communication modality, travel information/directions and safety concerns for potential home visits, and contact information of participants in the intervention group. The SHARE advance care planning facilitators will then contact person-family dyads using patient/family preferred mode of contact (e.g., by telephone or email) within 3 (+/- 3) business days of the enrollment visit to request either an in-person or remote meeting. Within 5 business days of receiving participant

information, the SHARE ACP facilitators/ interventionists will contact person-family dyads on their preferred mode of contact (e.g. by telephone or email) to request either a remote or in-person meeting. The meeting will ideally be scheduled within 4 weeks of the baseline assessment. The duration and nature of the conversation and the frequency and mode of subsequent contacts will be tailored to accommodate individual preferences. The initial advance care planning meeting is expected to be 45-60 minutes duration. In the initial meeting the facilitator will follow a semi-structured conversation guide and employ motivational interviewing techniques to stimulate interest, uptake, and adoption of SHARE components. Two copies of an ACP summary (F11) will be available via a letter delivered by post or email to patients assigned to the intervention for review at their leisure, and as a reminder of topics covered. From prior work^{47,74} we expect most older adults and families will be receptive to SHARE but that older adults and family caregivers will vary in readiness and capacity to engage in elements of advance care planning. For example, prior studies find persons with severe cognitive impairment (TICS-m≤27) may have the capacity to name a surrogate decision-maker but that completing an instructional directive to specify preferences for medical treatments will likely exceed decision-making capacity.^{75,76}

Existing asynchronous secure messaging features of the patient portal enable patients and individuals who have shared access to contribute to the electronic health record (e.g., to elaborate on meeting discussions, communicate emerging concerns, or summarize informal family conversations) to inform and stimulate ongoing discussions and documentation. This feature may be leveraged in communications with the interventionist. At the initial meeting the interventionist will clarify ongoing availability for follow-up meetings and seek patient and family input regarding the frequency (e.g., monthly, quarterly) and mode (by phone, via secure electronic messaging through the patient portal) of future “check-in” contacts to assess interest in scheduling future meetings. Subsequent in-person, telephone, or video conference meetings will occur as a result of “check-in” contacts initiated by the interventionist, ad-hoc requests by persons and/or family caregivers, or notable changes in health (e.g., unplanned hospitalization or emergency department visit, or notable change in health or function). SHARE interventionists will be expected to document the occurrence, content, and outcomes of advance care planning conversations after each ACP conversation (E5).

Participants may be asked to complete a brief questionnaire following all interventionist/facilitator meetings about their satisfaction with the conversation and their perception of its importance (E6, E7). Participants will be given the survey via web survey link or as a mailed paper form with a pre-addressed (to the study office or PI’s home address), stamped envelope return to the study team once completed.

6.2 FIDELITY

6.2.1 INTERVENTIONIST TRAINING AND TRACKING

Our approach to adherence assessment refers to how we monitor and maintain fidelity to the intervention protocol. Guided by the NIH Behavior Change Consortium⁷⁷ we address fidelity through a.) design, by selecting distinct therapeutic elements that are based on theory, b.) training, by relying on a protocolized curriculum to train interventionists in advance care planning and other elements of SHARE, c.) through multimodal assessment of the fidelity by which interventionists deliver the protocol, and d.) ongoing teleconferences at regular intervals (initially weekly, with less regular intervals over time as the interventionists gain competency) to monitor and support interventionists. All new interventionists will be required to present their first three cases during weekly case presentation meetings for discussion. The advance care planning facilitator (interventionist) will document all patient and family caregiver

contacts and advance care planning discussions in the patient's electronic health record and/or a REDCap data base (E5).

Interventionists will be nurse case managers, social workers, office medical assistants, community health workers who work 3 or more days per week and have been in their position for a minimum of one year, or trained lay facilitators hired by the study team. Training content will include all elements of SHARE, including: The Respecting Choices curriculum, documenting advance directives, facilitating family meetings, communicating difficult news, and assessing cognitive capacity. Training will be delivered and reinforced using traditional didactics, case scenarios and video conversations, and modeling and mentored role play. [name] will supervise interventionists in weekly telephone meetings initially with monthly meetings after.

We rely on an established curriculum, Respecting Choices <http://respecting-choices.org>, to train interventionists to lead advance care planning conversations. Respecting Choices includes patient and family education materials, a structured educational curriculum to train non-physicians in the competencies of advance care planning and standardization of policies for embedding ACP in routine care delivery.^{26,27} The Respecting Choices program includes 6 online modules with scripted interview tools and communication techniques to facilitate understanding ACP, exploring personal values, identifying a health care decision-maker, and communicating preferences for end-of-life care. Respecting Choices has been successfully delivered by a range of non-physician interventionists, including nurses, social workers, and lay navigators^{25,63} and has been well received in racially and ethnically diverse communities.^{78,79} Prior studies that have demonstrated benefit for advance care planning outcomes and reductions in per-capita costs of end-of-life care,^{25-27,63} have motivated the adoption of Respecting Choices by health care systems nationally and internationally.⁷⁸⁻⁸¹ However, Respecting Choices has not been specifically studied among persons with cognitive impairment or combined with strategies to proactively engage family caregivers in primary care, as we propose in this study.

Advance care planning facilitators will be either social workers, nurses, or medical assistants that are embedded in primary care as part of existing staff - or trained lay facilitators hired by the study team. Training will include all components of SHARE, including: certification in the Respecting Choices ACP curriculum, with specific attention to working with patients with cognitive impairment and families; documenting and uploading advance directives; resources specific to cognitive impairment and/or dementia. Training will be delivered and reinforced using traditional didactics, case scenarios and video conversations, and modeling and mentored role play.

6.3 MEASURES TO MINIMIZE BIAS

Most intervention research in primary care has relied on cluster-randomization at the level of the clinic, which leads to challenges in the interpretation of results due to practice-level imbalances and unmeasured contextual differences.⁶⁰ This study randomizes at the level of person-family dyad, which may lead to between-group spillover and attenuate observed intervention effects. However, as as many as 31 intervention dyads (+/- 5) will be enrolled at each clinic (~4/month), we do not expect widespread changes to standard clinic workflows or practices. We believe the possibility of contamination is low as the intervention consists primarily of one-on-one contact between the advance care planning facilitator and the person-family dyad, and there are no elements of the intervention that attempt to address clinicians' communication skill. Nevertheless, our analysis plan permits us to assess for the occurrence of contamination by evaluating whether there are changes over time in the control arm related to care processes, such as registration for shared access to the patient portal and advance directive completion.

Dyad-level randomization will afford a more nuanced understanding of context and allow examination of group differences by primary care clinic.

Each person-family dyad will be randomized to treatment or control group in a 1:1 ratio using stratified, blocked randomization by doctor with alternating block sizes of 4 and 6 for each clinician. A statistical program developed by the project statistician and unknown to study staff will be used to prospectively generate random treatment group assignment of study participants for each participating clinician. A set of opaque envelopes will be prepared for each clinician following the results of the statistical program. Upon providing informed oral consent (**B4, C2, D4**) and after completing the baseline enrollment survey (**B6, C3**), research staff will open the next sequentially ordered envelope specifying treatment group by clinician. Person-family dyads assigned to the treatment group will receive information about SHARE. Person-family dyads assigned to the control group will receive print materials about communicating with their doctor.

Research staff responsible for the randomization protocol after enrollment will be aware of participant assignment status after it occurs. Allocation concealment will be ensured by blinding the PI and research staff conducting follow-up assessments and those responsible for coding study outcomes throughout the study. Only the study statistician, selected unblinded staff (and REDCap administrator), and members of the data and safety monitoring board (DSMB) will have access to unblinded data before study completion. As randomization occurs at the level of the person-family dyad, clinicians will care for patients in both groups. Clinicians will be blinded to group assignment. Patient-family dyads will have knowledge of group assignment, but no delineation will be made between group assignment indicating which is treatment or control. We will use group naming conventions of (Group A and Group B) to describe group assignment.

6.4 STUDY INTERVENTION/EXPERIMENTAL MANIPULATION ADHERENCE

The approach to monitoring ongoing delivery of the intervention protocol will involve recording and auditing advance care planning sessions to determine the extent to which the protocol-based objectives are achieved. Following Vaccaro and Seaman,^{82,83} we will implement a fidelity audit tool to assess the extent of adherence of advance care planning conversations to the curriculum, and the competence of its delivery (**E10**).

We will evaluate the extent to which patients and family caregivers avail themselves to therapeutic elements of the intervention relating to advance care planning conversations and interactions with primary care clinicians and their team about wishes for future medical care and goals of care. A monthly report will be generated to track the number, duration, and mode of all contacts with the advance care planning facilitator, the content of advance care planning discussions, as well as registration for the patient portal by the patient and the family caregiver. The report will produce information by interventionist and by clinic site. This level of detail will permit the team to identify areas where full implementation is not being achieved and enable corrective actions. If potentially problematic content during meetings is noted, it will be flagged for review during supervision meetings. This information will be used to descriptively characterize the intervention group at each data collection time point and as it relates to outcomes. In this study we endeavor to complete at least one advance care planning discussion for each person-family dyad assigned to the intervention group; ideally within 4 weeks of the enrollment.

6.5 CONCOMITANT THERAPY

N/A

6.5.1 RESCUE THERAPY

N/A

7 STUDY INTERVENTION/EXPERIMENTAL MANIPULATION DISCONTINUATION AND PARTICIPANT DISCONTINUATION/WITHDRAWAL

7.1 DISCONTINUATION OF STUDY INTERVENTION/EXPERIMENTAL MANIPULATION

This is a Minimal Risk study of a behavioral intervention. The trial will be conducted in a population of older adults 80 years and older with cognitive impairment and the significance of our study rests in part on low completion of advance care planning in the target population despite high rates of mortality and adverse health events (e.g., hospitalization, emergency department visits). Advance care planning is already routinely offered in primary care and uptake of intervention processes will be at the discretion of patients and families. Participants will be free to terminate their participation at any time and will be reminded of this during the consenting process. Participants in the trial will be offered the intervention as a part of routine care and will be free to decline all aspects of intervention activities but will continue to be assessed according to intention to treat.

7.2 PARTICIPANT DISCONTINUATION/WITHDRAWAL FROM THE STUDY

We will monitor loss to follow up and discontinuation of participation in the study. Data from screening calls, intervention contacts and participant surveys will be entered into REDCap forms that the data manager will check for completion and accuracy. The data manager will provide semi-monthly reports of missing or inappropriate entries to the PI for clarification and resolution. Standardized electronic data validation checks will be developed within the database constructs using data entry discrepancy flags, programmed query rules, and in certain cases, external rules using SAS code. Monthly reports in aggregate and by study site will be generated summarizing accrual, completeness of follow-up, and study withdrawals. Periodic reports will be generated at the request of the Project Manager or the Principal Investigator. The Data Manager will generate all these reports, working collaboratively with the Biostatistician and study staff. The reason for participant discontinuation or withdrawal from the study will be recorded on the Case Report Form (CRF), tracked in REDCap, and reported to the DSMB. Subjects orally consent and are randomized but do not receive the study intervention may be replaced. Subjects who orally consent and are randomized and receive the study intervention, and subsequently withdraw, or are discontinued from the study will not be replaced.

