5.5.3 ENROLLMENT, BASELINE, AND/OR RANDOMIZATION

Enrollment officially occurs at the time of providing informed oral consent. See section 5.5.2 for more information about remote processes including enrollment and baseline assessment via telemedicine. For patient and family participants, enrollment occurs prior to completing the baseline assessment and randomization. The date of study enrollment will be tracked and documented for each participant.

Most intervention research in primary care has relied on cluster-randomization at the level of the clinic, which leads to challenges in the interpretation of results due to practice-level imbalances and unmeasured contextual differences.⁶⁰ This study randomizes at the level of person-family dyad, which may lead to between-group spillover and attenuate observed intervention effects. However, as 31 (+/- 5) intervention dyads will be enrolled at each clinic (~4/month), we do not expect widespread changes to standard clinic workflows or practices. We believe the possibility of contamination is low as the intervention consists primarily of one-on-one contact between the interventionist and the person-family dyad, and there are no elements of the intervention that attempt to address clinicians' communication skill. Nevertheless, our analysis plan permits us to assess for the occurrence of contamination by evaluating whether there are changes over time in the control arm related to care processes, such as registration for shared access to the patient portal and advance directive completion. Dyad-level randomization will afford a more nuanced understanding of context and allow examination of group differences by primary care clinic.

Each person-family dyad will be randomized to treatment or control group in a 1:1 ratio using stratified, blocked randomization by doctor with alternating block sizes of 4 and 6 for each clinician.

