7.3 LOST TO FOLLOW-UP

A participant will be considered lost to follow-up if study staff are unable to contact the participant after at least 15 attempts for the 6-month, 12-month, or 24-month follow-up survey.

The following actions must be taken if a participant is unreachable by study staff:

[figure not shown]
- Study staff will seek to contact family of an unreachable patient, or the patient of an unreachable family.
- Study staff will query the electronic health record or ask primary care clinic staff if the patient has moved or had a change in health status.
- If these efforts are not successful, the participant will be noted as having been lost to follow up.

If a patient/family dyad are lost to follow-up, we will use all available data that are observed on that dyad in analyses. For patients who are lost to death, we will attempt bereavement surveys with family caregivers two to three months after death, following best practices.

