9.4 STATISTICAL ANALYSES

9.4.1 GENERAL APPROACH

Quantitative Strand. The objective of this study is to test the efficacy of SHARE on quality of communication (QOC) at 6 months. Analyses will be performed using SAS statistical software, with each dyad as the unit of analysis. We will use intention-to-treat analyses as the primary method of analysis; data from all participants will be analyzed as members of their assigned study group. **Primary outcome:** We will test the effects of SHARE on improved QOC compared to usual care at 6 months. We will use hierarchical analyses of covariance on the 6-month (**B7, C4**) QOC score with treatment group as the primary independent variable and baseline QOC score as the primary covariate. Other baseline characteristics (individual- or practice-level variables) will be covariates if there is imbalance on these measures by treatment group or if they are significantly correlated with 6-month QOC after adjusting for baseline QOC score. A multilevel design will be implemented using SAS Proc MIXED with dyads (level 1) nested within clinics (level 2) that will allow us to enter and control for clinic-level covariates (size and characteristics of patient panel, staff, location). **Secondary outcomes and supplemental analyses:** In addition to the primary outcome, numerous comparisons will be conducted for secondary outcomes, measures of implementation, and supplemental analyses for clinically relevant subgroups and maintenance of effects at 12 and 24 months. We will examine the maintenance of intervention effects at 12 (**B8, C6**) and 24-months (**B9, C7**) by extending the multilevel model to include a longitudinal or within-person level, and trajectories of treatment impact over time will be estimated with linear longitudinal models.

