10.1.2 STUDY DISCONTINUATION AND CLOSURE

This is a Minimal Risk study of a behavioral intervention. The trial will be conducted in a population of older adults 80 years and older with cognitive impairment and the significance of our study rests in part on low completion of advance care planning in the target population despite high rates of mortality and adverse health events (e.g., hospitalization, emergency department visits). Advance care planning is already routinely offered in primary care and uptake of intervention processes will be at the discretion of patients and families. Participants will be free to terminate their participation at any time and will be reminded of this during the consenting process. Participants in the trial will be offered the intervention as a part of routine care and will be free to decline all aspects of intervention activities but will continue to be assessed according to intention to treat.

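### Does letting randomized dyads who do not receive the intervention be replaced (section 7.2) break the intention-to-treat comparison?

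*Combined protocol and SAP*

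**What the plan says.** Section 7.2 deals with discontinuation and withdrawal. It reads "Subjects orally consent and are randomized but do not receive the study intervention may be replaced", and then says that those who received the intervention and later withdrew are not replaced. It does not define receipt and does not mention intention to treat.

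The rules on follow-up and analysis are elsewhere:

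- Section 7.1: participants "will be free to decline all aspects of intervention activities but will continue to be assessed according to intention to treat". Section 10.1.2 repeats this.
- Section 9.4.1: "data from all participants will be analyzed as members of their assigned study group", and the analysis is "with each dyad as the unit of analysis".
- Section 7.3, for a dyad lost to follow-up: "we will use all available data that are observed on that dyad in analyses". Section 8.1 says the same.
- Section 9.2 bases the sample size on intention to treat.
- Section 5.5.3: "Each person-family dyad will be randomized to treatment or control group in a 1:1 ratio using stratified, blocked randomization by doctor". Section 6.3 describes the step at the clinic: "research staff will open the next sequentially ordered envelope specifying treatment group by clinician".

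On uptake, section 6.4 aims for at least one advance care planning discussion per SHARE dyad and sets up monthly tracking of contacts. The fidelity rows of the 9.3 table include a yes/no item for having had at least one such discussion.

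**The concern.** Replacing randomized participants is a familiar warning sign. If the replaced participant leaves the analysis, the groups compared are no longer those that randomization formed.

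Two features make it look worse here. First, SHARE is a bundle of a letter, printed materials, agenda-setting, access to a facilitator and help with the portal. A dyad that was sent the materials but refused every meeting is a receiver on one reading and a non-receiver on another. Second, the control arm gets only a letter, a brochure and a blank directive, so a control dyad can hardly fail to receive its protocol. Replacement would therefore fall almost wholly on the SHARE arm. If SHARE dyads that avoid the discussion also tend to report poorer communication, removing them would flatter SHARE.

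Section 7.2 can also seem to clash with 7.1: the same dyad, having declined everything, is kept under one section and replaceable under the other.

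**Working it through.** **1. The plan's own figure.** Inputs from section 9.2: unadjusted effect 0.30 SD, baseline correlation 0.65, 248 dyads enrolled, 10% attrition, 222 retained, two-sided 0.05.

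- Adjusted effect: 0.30 / sqrt(1 − 0.65²) = 0.30 / sqrt(0.5775) = 0.395 (stated 0.39).
- Retained: 248 × 0.9 = 223.2 (stated 222).
- Power: shift = 0.39 × sqrt(222/4) = 2.905; P(Z > 1.96 − 2.905) = 82.8%, in line with the stated value of more than 80%. With 0.395 it is 83.7%.

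The sample size holds and does not rely on replacement.

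**2. What happens to a replaced dyad.** There are two cases.

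- *It declines the activities but stays in the study.* Sections 7.1 and 10.1.2 keep it under assessment, and 9.4.1 analyses it in its assigned arm. Nothing in 7.2 removes it.
- *It leaves the study before receiving anything.* Its 6-month score is missing whether or not another dyad is recruited. Replacement does not create that gap, and 9.2 allows for attrition.

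In both cases the replacement is a new enrolment. Sections 5.5.3 and 6.3 describe different mechanics (REDCap and envelopes), but under either the new dyad takes the next allocation for its clinician, at 1:1. It may fall in either arm. Section 9.4.6 plans no interim analysis, so recruitment is not steered by outcomes. Replacement itself adds no bias.

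**3. Size of the top-up.** Because allocation is 1:1, restoring k SHARE dyads takes about 2k enrolments. For k = 10 that is 20, giving 248 + 20 = 268, the upper end of the planning range in sections 1.1 and 5. That range is approximate and is not stated as a cap.

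**4. The reading that would do harm.** Suppose, against the text, that a share q of SHARE dyads were replaced and dropped, and that they would have scored g adjusted SD below the other SHARE dyads. The documents give neither q nor g, so both are assumptions. Under no true effect the bias is q × g, with standard error sqrt(2/111) = 0.134.

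| q | g | Bias (SD) | Two-sided type I error |
|---|---|---|---|
| 10% | 0.25 | 0.025 | 5.4% |
| 10% | 0.75 | 0.075 | 8.7% |
| 20% | 0.25 | 0.050 | 6.6% |
| 20% | 0.75 | 0.150 | 20.1% |

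This could matter, but it needs a dropping rule that the plan never states and that 9.4.1 contradicts.

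**5. Power when non-receivers are kept.** Assume 10 of 124 SHARE dyads receive nothing and gain nothing.

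- No top-up: effect 0.39 × (1 − 10/124) = 0.359; shift 0.359 × sqrt(222/4) = 2.67; power about 76%.
- Topped up to 268 (268 × 0.9 = 241 retained, 134 in SHARE): effect 0.39 × (1 − 10/134) = 0.361; shift 0.361 × sqrt(241/4) = 2.80; power about 80%.

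If 0.39 already allows for incomplete uptake, power stays at 82.8% without a top-up. The documents do not say which applies. On the first assumption the top-up recovers some power, which is a legitimate reason for the provision.

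**The case for a change.** The best case for a change is that retention of replaced dyads is inferred from other sections. Section 7.2 is the one that staff will use when a dyad drops out, and someone reading it alone might stop following a dyad once it had been replaced. Because the rule bites almost only in the SHARE arm, such a lapse would be one-sided, and a sentence or two would rule it out.

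Some of this stands. Section 7.2 is silent on follow-up, the asymmetry between arms is real, receipt has no counterpart in the control arm, and subjects should read dyads.

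It does not amount to a flaw in the design or analysis. The section is operational and defines no analysis set; the intention-to-treat rule is stated in 7.1, 9.4.1 and 10.1.2. The apparent clash with 7.1 also has a natural resolution. Section 7.2 is headed discontinuation and withdrawal, and its next sentence concerns people who withdraw after receipt, so the replacement sentence fits those who leave before receipt. That reading is not certain, since the sentence does not itself mention withdrawal, but retention follows from 7.1 and 9.4.1 even if it is wrong.

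Reporting is largely covered as well: the 9.3 table has the yes/no discussion item and a CONSORT diagram, 9.4.1 compares attrition between arms, and 7.2 sends reasons for discontinuation to the DSMB. Sections 5.5.3, 7.3 and 9.4.1 settle the unit as the dyad.

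**Conclusion.** No change is needed. Following the stated rules, every randomized dyad stays in its assigned arm for analysis, replacement is further enrolment through the normal allocation, and the bias from replacement itself is nil. Ordinary missing data remain, as in any trial with attrition. The planned power reproduces at 82.8%. If non-receivers are kept and gain nothing, power could fall to about 76%; that is dilution from non-uptake and not a consequence of 7.2.

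The conclusion rests on reading 7.2 together with 7.1, 9.4.1 and 10.1.2, which is how an analyst would work. It would fail only if replaced dyads were dropped in practice, contrary to those sections. What is left is missing detail and a loose word, with no effect on the primary result.
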